## STUDY PROTOCOL

Subjects will be recruited from referrals by Dermatologists at Stanford Hospital and clinics, via self-referrals from recruitment flyers and from the Stanford Dermatology Clinics Stanford Hospital and clinics hyperhidrosis patient population. Patients will be screened for eligibility either in person during a routine clinical visit or over the phone.

The study will consist of 3 treatment phases (daily treatment for 2 weeks, 3x/week treatment for 3 weeks and 2x/week treatment for 3 weeks) and a post-treatment evaluation.

During the daily treatment phase, the subject will perform sweat level assessments and deliver treatment during office visits (1 in person and 1 virtual in this phase) and daily at home. The sweat level assessments will include gravimetry (in-office), visual assessment, iodine imprint testing (at home and in-office), and a study diary (at home and in-office), all commonly used methods to assess sweat levels for research purposes. Treatment will consist of 30 -60 minutes of hydrogel-based iontophoresis. During the three-time per week and two-time per week phases, the patients will undergo the allocated amount of treatments per week, perform iodine imprints at home and complete a study diary. There will be one office visit at the start of the 3x/week phase. The post-treatment evaluation will take place as an office visit.

The first visit will be used to explain the study protocol, obtain informed consent, assess disease severity with baseline sweat level assessments, determine treatment settings, and provide training on performing the treatment and a study diary at home. Sweat level assessment will be obtained using gravimetry (quantitative measurement of sweat production by weight over a specified time period), iodine imprint testing (topical application of an iodine solution to qualitatively visualize sweat production after making an imprint on paper), and completion of a study diary. Study diary entries consist of a hyperhidrosis disease severity scale (HDSS) score (modified to reflect the severity of symptoms over a single day, visual pain assessment (Wong-Baker pain scale), and a prompt to specify general comments or any side effects related to the treatment. Treatment will consist of delivering a low level of direct electrical current to the palmar side of one hand.

In line with standard tap water iontophoresis, amperage will be increased manually by the patient until the tingling induced by the current is at the upper limit of comfort. The current level will not be increased beyond 20 mA regardless of patient's tolerance. The treatment may not be effective below a minimal therapeutic level (R.A. Fischer MD-2 manual). Therefore, if the subject finds low levels of current intolerable (e.g. below 6ma), the investigators may decide to exclude the subject from the study. The treatment duration will be up to 1 hour, consistent with

what commercial devices are able to sustain (Hidrex DVP1000 user manual).

During the various treatment phases, the subject will be asked to perform the following tasks independently at home: deliver treatments daily, triweekly or biweekly for a period of 2-3 weeks each, complete a daily questionnaire/study diary, and perform iodine imprint testing at least twice per week. Data will be collected through a REDCap survey. The patient will also be asked to photograph and store the paper imprints in a dedicated folder.

A second contact point will be scheduled virtually within 2-4 days of the first visit to ensure that the subject is correctly performing the treatment, and to provide any additional training needed.

After the end of the daily treatment phase (day 14, 15, 16 or 17), the subject will return to the office to perform treatment, complete gravimetry and iodine imprint sweat level assessments.

The subject then enters treatment phases with decreased treatment frequency to 3x/week for 3 weeks and 2x/week for 3 weeks. They will return to the office for a final evaluation visit and study wrap-up (day 56, 57, 58 or 59).

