#### STATISTICAL ANALYSIS PLAN

We will be assessing the difference in sweat levels between the hands using gravimetry, iodine imprint testing, and symptom questionnaires. Gravimetry is commonly used in research settings to quantify sweat levels. Filter paper is weighed before and after application to the palmar surface of the hand for a fixed duration in time, e.g. 5 minutes. The weight difference quantifies the amount of sweat produced over a period of time (in mg/min). We will follow up changes in sweat levels based on data uploaded through REDCap. After the study the Student's t-test will be used to assess sweat levels between the treated and untreated hands.

Iodine paper imprint testing is a documented method to qualitatively assess sweat levels. The hands are cleaned and dried prior to application of iodine solution to the palmar sides of the hands. After the iodine solution has dried, subjects will apply steady pressure with their palms onto a sheet of paper. Sweat in contact with iodine and starch will produce a colorimetric change, with a purple-black color on the paper indicating the presence of sweat on the hands. The subject will take a photograph of this paper as a baseline qualitative measure of sweating and upload this onto the REDCap system through the survey diary. We will follow up changes in sweat levels on a daily basis based on data

uploaded through REDCap. Differences in iodine imprint testing results between the left and right hand, and changes over the course of the study, will be assessed visually by a member of the research staff. After the study we will try to quantify the difference in sweat levels between the hands using image analysis software (e.g. ImageJ).

Subjects will complete a survey diary with questions based on the Hyperhidrosis Disease Severity Scale (HDSS), a sweat assessment that is commonly used in hyperhidrosis studies. Modifications that we have made to the HDSS include distinguishing symptom severity of each hand and assessing overall symptom severity on a single day. Study diary responses will be reviewed by a member of the research staff on a daily basis

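### The daily pain score has no stated timing and no session marker while sessions fall from 7 to 3 to 2 a week, so pain cannot be reliably tied to sessions or compared across phases; the side-effect wording also has the subject judge causality first

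*Combined protocol and SAP*

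**What the plan says.** The diary contents are listed in the STUDY PROTOCOL section: an HDSS score modified to cover a single day, and a "visual pain assessment (Wong-Baker pain scale), and a prompt to specify general comments or any side effects related to the treatment". Among their home tasks during the treatment phases, subjects are to "complete a daily questionnaire/study diary". The phases are "daily treatment for 2 weeks, 3x/week treatment for 3 weeks and 2x/week treatment for 3 weeks". Treatment means "delivering a low level of direct electrical current to the palmar side of one hand", and "amperage will be increased manually by the patient until the tingling induced by the current is at the upper limit of comfort", subject to a stated ceiling.

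The STATISTICAL ANALYSIS PLAN section anchors the HDSS more closely: "Modifications that we have made to the HDSS include distinguishing symptom severity of each hand and assessing overall symptom severity on a single day". It gives no such anchor for pain. Its stated aim is: "We will be assessing the difference in sweat levels between the hands using gravimetry, iodine imprint testing, and symptom questionnaires". It describes no summary of pain or of side effects. It does provide for regular oversight: "Study diary responses will be reviewed by a member of the research staff on a daily basis".

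**The concern.** A pain score needs a reference: during the current, afterwards, over the whole day, or at the moment the form is opened. None is stated. In the daily phase this matters less, because every diary day should be a session day. In the two later phases most diary days have no session, the text fixes no weekdays for sessions, and the listed diary contents include no item saying whether one took place. An analyst would then have no sure way of telling which scores describe a session.

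The patient sets the current at the edge of comfort, so discomfort during sessions is an expected part of using the device. Apart from a virtual contact in the first days and the visit at the end of the daily phase, the diary is the only described source of tolerability data until the final visit. A simple phase average would mix how much a session hurts with how often sessions occur, and could make tolerability look better as sessions become less frequent.

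The second issue is the side-effect prompt. A subject who does not connect a skin change or symptom with the device is not directly asked about it.

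**Working it through.** The documents give no pain figure, so there is nothing of theirs to reproduce. The check asks how far an all-day average could move if pain per session stayed constant.

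**Inputs from the STUDY PROTOCOL section:** 7 sessions a week for 2 weeks, 3 a week for 3 weeks, 2 a week for 3 weeks; diary completed daily.

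**Step 1: share of diary days with a session.**
- Daily phase: 7 × 2 = 14 sessions over 14 days, 100%.
- Three-a-week phase: 3 × 3 = 9 sessions over 21 days, 42.9%.
- Two-a-week phase: 2 × 3 = 6 sessions over 21 days, 28.6%.

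**Step 2: mean over all diary days.** Let s be sessions per week, P the session-day score (constant throughout) and q the off-day score as a fraction of P. Then

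mean = [s·P + (7 − s)·q·P] / 7

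The daily phase gives P, so the proportional fall from that phase is (1 − s/7)(1 − q). P cancels, so the percentages do not depend on the score assumed, but they do depend on q.

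**Step 3: results.** P and q are assumptions, since the documents give neither. P = 4 is used for illustration and q is varied over its range from 0 to 1.

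| Off-day pain | Daily | 3 a week | 2 a week | Falls from daily phase |
|---|---|---|---|---|
| q = 0 | 4.00 | 4 × 3/7 = 1.71 | 4 × 2/7 = 1.14 | 57%, 71% |
| q = 0.5 | 4.00 | (12 + 8)/7 = 2.86 | (8 + 10)/7 = 2.57 | 29%, 36% |
| q = 1 | 4.00 | 4.00 | 4.00 | none |

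**Step 4: other summaries.** A mean over session days only is P in every phase, so the artefact disappears, but it requires knowing which days were session days. A weekly maximum is also P in every phase if q is at most 1 and at least one session took place that week, but it discards the other sessions.

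**The case against.** The strongest reply is that the apparent fall belongs to an analysis nobody has planned. The SAP commits to sweat comparisons between the hands and names no pain average or comparison across phases. That stands. A reader might infer that reported pain is bound to fall across phases, or that the item measures session frequency instead of pain. The documents support neither. The fall needs an all-day average together with lower off-day pain, and a score given on a session day may well describe that session. The trouble lies in linking and summarising the scores.

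A reader might also infer that side effects not blamed on the device are shut out and will be under-reported. That goes too far: the same prompt invites general comments, and staff read the entries daily. What remains is that no described question asks for all events whatever their cause.

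Two further points are fair. Only one hand is treated, so session pain most naturally refers to that hand, and the missing hand reference is minor. The REDCap form is not in the documents and may already record sessions or timing; if so, the protocol need only say so.

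The reply that an analyst can simply restrict to session days does not settle the matter. With no session marker described and no fixed weekdays, the restriction may not be possible once the data are in. Even with a marker, a score without a reference period could mean pain during the current, soreness later, or pain at the time of entry.

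**Conclusion.** The point holds as a gap in what is collected and in how it would be summarised. As described, pain scores cannot be reliably tied to sessions in the two reduced-frequency phases, and this cannot be fully repaired after collection. The possible distortion in an all-day average runs from none (q = 1) to falls of 57% and 71% (q = 0), with 29% and 36% at q = 0.5. These figures assume constant session pain, the planned number of sessions in each phase, and a diary entry every day. They show what one unplanned but natural summary could do, and do not predict what the trial will report. The side-effect point is smaller: the subject makes the first judgement of causality, with general comments as a partial safeguard. Both are worth correcting because the changes are cheap before data collection.

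**What to change.** In the diary:
- Keep the pain item on every day. Showing it only on session days would lose delayed or persisting pain.
- Add one yes/no item: *Did you have a treatment session today?*
- Word the pain item as *worst pain in the treated hand during or since the session*, or *worst pain in the treated hand today* on days without a session.
- Reword the prompt to ask for *any symptom or skin change, whether or not you think it is due to the treatment*. Staff then judge relatedness at the daily review they already carry out.

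In the SAP, add a line stating that pain will be summarised separately for session days and non-session days within each phase, and a line on how side effects will be listed.

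If the existing form already contains any of this, describing it in the protocol is enough. The cost is one extra diary item, a few wording edits in REDCap, and some unrelated complaints for staff to sort. Treatment and visits do not change.

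### The plan does not say how the treated hand is chosen, and its only named test states neither pairing nor use of the baseline between-hand difference

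*Combined protocol and SAP*

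**What the plan says.** In the STUDY PROTOCOL section, the description of the first visit states: "Treatment will consist of delivering a low level of direct electrical current to the palmar side of one hand". Nothing there or in the rest of the protocol text mentions randomisation, handedness, a fixed side, the more affected hand, or who decides. The same visit is used to "assess disease severity with baseline sweat level assessments, determine treatment settings", so baseline sweating can be known before the hand is picked.

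The STATISTICAL ANALYSIS PLAN opens with "We will be assessing the difference in sweat levels between the hands using gravimetry, iodine imprint testing, and symptom questionnaires". The only named test is in its gravimetry paragraph: "After the study the Student's t-test will be used to assess sweat levels between the treated and untreated hands". The SAP does mention change. For gravimetry it says "We will follow up changes in sweat levels based on data uploaded through REDCap", and for the iodine imprints it says that between-hand differences "and changes over the course of the study, will be assessed visually by a member of the research staff". The diary version of the HDSS is modified by "distinguishing symptom severity of each hand". The sentence naming the test, however, refers to levels. It does not say that the test is paired or that the baseline difference between hands enters it.

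Material placed before the STUDY PROTOCOL section was not available, so these statements cover the protocol and SAP text only.

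**The concern.** No other control group is described, so how a hand becomes the control decides whether the comparison is valid. A choice linked to sweating, dominance or side can bias the result in either direction:

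- **Worse hand treated, follow-up levels compared** (the test as worded): the treated hand starts wetter, so benefit is hidden.
- **Worse hand treated, change scores compared:** part of the baseline excess is chance and recedes at follow-up, so benefit is exaggerated.
- **Better hand treated:** both signs reverse.
- **Same side always treated:** any natural left–right or dominance asymmetry enters the levels as a constant offset, for or against the device depending on which side is drier.

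The SAP names a test on levels but also speaks of following changes. The direction of bias therefore cannot be known beforehand or argued away afterwards. Separately, if the t-test is run as a two-sample test, it ignores the correlation between a person's two hands and loses most of its power.

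**Working it through.** The plan states no sample size, SD, correlation, asymmetry, effect size or alpha, so it has no figure to reproduce. Everything below is a hypothetical example.

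**Assumptions.** D is the treated-minus-untreated difference in sweat level, scaled to SD 1 at each visit. A positive value means the treated hand is wetter. The correlation r of D between baseline and follow-up is 0.3–0.7. There are 10–20 subjects and the test is two-sided at 5%. Each simulated cell uses 100,000 trials.

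**Bias when the worse hand is treated, no true effect.** The mean absolute value of a standard normal variable is √(2/π) = 0.798, which is the mean baseline difference if the worse hand is always chosen.

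- Levels: r × 0.798 = 0.24 (r = 0.3) to 0.56 (r = 0.7) SD against the device.
- Change: (1 − r) × 0.798 = 0.56 (r = 0.3) to 0.24 (r = 0.7) SD in favour of the device.
- Worse hand treated in 70%: multiply by 0.7 − 0.3 = 0.4. This gives 0.10–0.22 SD on levels and 0.22–0.10 SD on change.

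**False-positive rates, paired t-test, no true effect**

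| How the hand is chosen | Levels: favours untreated hand | Change: favours device |
|---|---|---|
| Worse hand always | 10.2% (n = 10, r = 0.3) to 82.2% (n = 20, r = 0.7) | 14.8% (n = 10, r = 0.7) to 62.4% (n = 20, r = 0.3) |
| Worse hand in 70% | 4.6–16.7% | 5.4–13.1% |
| Random | 2.4–2.7% | 2.4–2.7% |

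**Power for a true benefit of 0.8 SD, paired t-test on levels.** Random hand: 61.6% (n = 10) to 92.4% (n = 20). Worse hand in 70%: 38.4–85.0%. Worse hand always: 13.7–68.8%.

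**If the test is unpaired.** With between-hand correlation ρ, the unpaired standard error is 1/√(1 − ρ) times the paired one: 1.83 times at ρ = 0.7 and 3.16 times at ρ = 0.9. Power with a random hand is then 0.9–47.4%, against 61.6–92.4% paired. The false rate against the device also shrinks, to 0.01–13.4% (worse hand always) or at most 0.8% (70%), because the test is too conservative.

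**Adjusting for the baseline difference.** Regress follow-up D on baseline D and test the intercept. With a random hand this gives 2.4–2.6% per direction and power of 59.6% (n = 10, r = 0.3) to 99.5% (n = 20, r = 0.7).

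**Does adjustment alone suffice?**

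- *Worse hand always treated:* the error rate holds at about 2.5% per direction, but power is 27–78%.
- *One side always treated, natural asymmetry 0.25–0.5 SD:* on levels the test is a non-central t with non-centrality asymmetry × √n. That is 0.25 × √10 = 0.79 to 0.5 × √20 = 2.24, for a two-sided false rate of 11–56%. After adjustment an offset of asymmetry × (1 − r) remains, from 0.25 × 0.3 = 0.075 to 0.5 × 0.7 = 0.35 SD, and the false rate is 5.9–27.7%. With a random hand it is about 5%.

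These cases are alternatives and must not be added.

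**Second variance model.** This used between-subject SD 1, measurement SD 0.3 per hand, true between-hand SD 0.2 or 0.5, and n = 10–30. It gave the same directions. Treating the worse hand shifted levels by +0.07 to +0.31 and change by −0.22 to −0.31. Treating the better hand reversed the signs. Randomising removed the bias.

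**The case against.** Nothing in the documents suggests that the hand will be chosen by sweating, and the investigators may have an unwritten rule. The largest figures need two things together: the worse hand treated in every subject, and a paired test that the SAP does not state. Under milder selection or an unpaired test the false-positive rates are much smaller. A range of 10–82% says little about this particular trial, and without a stated alpha or primary endpoint the t-test may not be meant as a decision rule.

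Each bias also has an analysis-only remedy. Baseline adjustment restores the error rate when the hand is chosen on measured sweating. A change score removes a stable side offset (about 5% two-sided in simulation).

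The point about size stands: the percentages illustrate and do not predict. The point about remedies is correct but does not remove the need to randomise. Adjustment fails for a fixed side, change scores fail under worse-hand selection, and no single analysis covers both. Where adjustment does hold the error rate under worse-hand selection, it gives up much of the power.

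It is also fair that a baseline covariate presupposes gravimetry on both hands at the first visit, which the text implies but does not spell out. A revised SAP must also say which follow-up visit is tested.

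**Conclusion.** The concern holds. The protocol and SAP give no rule for allocating the treated hand, and the only named test is a comparison of levels without stated pairing or baseline adjustment. The two-way direction of the bias follows from the design and does not depend on the assumed parameters. Its size does: under the assumptions above, the false-positive rate in one direction can run from about 5% with partial worse-hand selection to over 80% with complete selection and a paired test on levels. Random allocation brings it to about 2.5%.

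Confidence is high that the rule is absent from the text reviewed and that the comparison is exposed. The sizes are hypothetical. The plan should be changed on this point.

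**What to change.** **Protocol, first visit.** Add, for example: *Gravimetry is recorded on both hands at baseline. The hand to be treated (dominant or non-dominant) is then allocated 1:1 at random from a concealed computer-generated list and stays fixed for all three treatment phases. Handedness is recorded.*

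**SAP, gravimetry.** Add: *The t-test is paired within subject. The treated-minus-untreated difference at the named follow-up visit is regressed on the baseline treated-minus-untreated difference, not mean-centred, and the intercept is tested as the treatment effect.* If the covariate were mean-centred, the intercept would return the unadjusted mean difference. The visit must be named. The protocol lists gravimetry explicitly at the office visit on day 14–17 but does not list it for the final visit on day 56–59. Blocking the list would limit chance imbalance in dominance; this affects precision, not validity.

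**Cost.** A short amendment and a concealed list, which may have to be held outside REDCap because the documents describe REDCap only for surveys and uploads. Baseline gravimetry is already planned, so no new data are needed provided both hands are measured. The covariate uses one degree of freedom: in the least favourable cell (n = 10, r = 0.3), power is 59.6% instead of 61.6%. Some subjects will treat the hand they would not have picked.

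**What it leaves open.** Randomising the hand does not mask the subject or the staff. No masking is described for the diary scores or the visual reading of imprints, so those outcomes keep a separate risk of bias.

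### Could the undated low-current exclusion remove treated subjects from the analysis and bias the comparison between hands?

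*Combined protocol and SAP*

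**What the plan says.** The relevant text is in the STUDY PROTOCOL, in the account of how current is set. At each treatment "amperage will be increased manually by the patient until the tingling induced by the current is at the upper limit of comfort", with a ceiling of 20 mA. The reason for the exclusion comes next: "The treatment may not be effective below a minimal therapeutic level". For a subject who finds low current intolerable, with 6 mA as an example, "the investigators may decide to exclude the subject from the study". No visit or day is attached.

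Earlier in the same section, the first visit is used to obtain consent, "assess disease severity with baseline sweat level assessments, determine treatment settings" and train the subject for home use. After that visit, "A second contact point will be scheduled virtually within 2-4 days of the first visit". At home the subject is to "perform iodine imprint testing at least twice per week" and complete a daily diary. After the daily phase (day 14 to 17), "the subject will return to the office to perform treatment, complete gravimetry and iodine imprint sweat level assessments". For the end of the study (day 56 to 59) the text says: "They will return to the office for a final evaluation visit and study wrap-up".

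The STATISTICAL ANALYSIS PLAN names a Student's t-test comparing the two hands. It defines no analysis set and does not mention reporting exclusions. It also has research staff review diary responses daily and judge the imprints by eye.

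**The concern.** Three features together look troublesome. The exclusion is discretionary and undated. Its stated reason is expected lack of efficacy, so it selects on a presumed predictor of outcome. And staff see hand-level information during treatment (imprints and per-hand HDSS scores), with no blinding of that review described.

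If the rule were used after home treatment began, the subjects removed would tend to be those in whom the device works least. Removal before day 14 would also keep them out of gravimetry, the measure for which the t-test is named. The mean difference between hands would then describe people who tolerate the current and would overstate the effect among everyone who started. With no analysis set and no stated count of exclusions, a reader of the results might not be able to tell.

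**Working it through.** The documents give no sample size, effect size, standard deviation or dropout rate, so there is no planned figure to reproduce. The check has three parts.

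**1. When does the rule apply?** The order of the STUDY PROTOCOL is informative:

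- The first-visit paragraph lists determining treatment settings among its tasks and ends by describing current delivered to one hand.
- The next paragraph continues that subject: raising the current to comfort, the ceiling, the low-current exclusion, treatment duration.
- Only then does the text move to home tasks, the virtual contact and the day 14 to 17 visit.

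The exclusion therefore sits inside the account of setting up treatment and before any home activity. The later contacts are not tied to it. The virtual contact is there to check technique and add training. The diary records a modified HDSS, pain, and comments or side effects; no current level is listed.

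**2. What follows if it is used at set-up?** No post-treatment outcome exists, so the decision cannot depend on one. The subject never becomes a starter, and the mean effect among starters is unchanged. Only the population described is narrower. Because one hand is treated and the other is the control, both leave together and the within-person contrast stays valid for those who remain.

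**3. What follows if it is used later?** Take a subject excluded on day 7, as an illustration:

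- imprints at a minimum of two per week: 2 × 7/7 = about 2
- daily diary entries: up to 7
- post-baseline gravimetry, first named at day 14 to 17: 0

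Such a subject would be missing from the gravimetry t-test. For the size of the distortion, let *p* be the share of starters excluded later and *r* their effect relative to that of the others. If the others have effect *d*, the mean among all starters is *d*[(1 − *p*) + *pr*], and the mean among those kept is *d*. The ratio is

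1 / [(1 − *p*) + *pr*]

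| *p* | *r* = 0 | *r* = 0.5 | *r* = 1 |
|---|---|---|---|
| 0.02 | 1/0.98 = 1.02 | 1/0.99 = 1.01 | 1.00 |
| 0.05 | 1/0.95 = 1.05 | 1/0.975 = 1.03 | 1.00 |
| 0.10 | 1/0.90 = 1.11 | 1/0.95 = 1.05 | 1.00 |

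Both *p* and *r* are assumptions. At *p* = 0.20 and *r* = 0 the ratio would be 1/0.80 = 1.25, but that requires one starter in five to be excluded late with no benefit in any of them.

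**The case for a change.** The best case for acting is that nothing in the text confines the exclusion to the first visit. Patients set their own current and treat unsupervised, so intolerance could emerge at home. Staff would then decide with hand-level results in view. If exclusion followed poor observed results, *r* could fall below zero, so the *r* = 0 column is not a strict upper bound. If the study is small, which the documents do not say, one late exclusion among 10 starters already makes *p* = 0.10. A few sentences would close the gap.

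Much of this is correct as a reading of the words: no time limit is written, no analysis set is defined, and no count of exclusions is promised. What does not carry over is the inference to bias. No text links the virtual contact or the diary review to exclusion, so the late route has no described mechanism. Silence about counting is not a decision not to count.

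The stronger remedies also exceed the evidence. Requiring anyone who stops later to remain for follow-up would replace a participant-management rule that the protocol leaves to the investigators. It would still not recover a subject who declined to return for gravimetry. What the final visit should measure is a separate question.

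**Conclusion.** The concern does not call for a change. On its natural reading, the exclusion is a set-up screen applied before any post-treatment outcome exists. It then adds no bias among those treated and limits only whom the result describes. This rests on the order of the text and on treatment settings being a first-visit task; the documents do not state it outright.

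If the rule were used later, the overstatement would be 1% to 11% for *p* from 0.02 to 0.10 and *r* from 0 to 0.5, and none at *r* = 1. The upper figure needs one starter in ten to be excluded late with zero effect in each. Neither input comes from the documents.

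What remains is ordinary missing detail. An analyst would normally include every subject who started home treatment and has post-treatment data, whatever current was reached, and would report exclusions with number, timing and reason. Nothing in the plan prevents that.
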